Two groups of 6-8 week old C57BL/6 male mice were vaccinated intramuscularly with 5×10^9 vp of the pre-clinical stock of ChAdOx1.5T4 vaccine and 5×10^9 vp of the clinical grade vaccine. For additional information, two sets of 5 mice were vaccinated with 5×10^8 vp and 5×10^7 vp per mouse. Thirteen days later the mice were sacrificed and the spleens harvested for an ex-vivo IFN γ ELISPOT assay. This assay demonstrated that ChAdOx1.5T4 elicited a strong cellular immune response, with all mice responding, at all three doses tested (Figure 4). The assay showed equivalent immunopotency of the pre-clinical stock and clinical grade vaccines (Figure 5).

Figure 4. Murine spleen IFN γ ELISPOT assay after ChAdOx1.5T4 vaccination: dose response

[figure not shown]
[figure not shown]

Figure 5. Immunopotency of ChAdOx1.5T4 pre-clinical Stock and clinical batch at 5 x 10⁹ vp dose

Safety of the clinical grade ChAdOx1.5T4 batch

[figure not shown]
A GLP repeat dose toxicity study of the ChAdOx1.5T4 vaccine has been performed at the Huntingdon Life Sciences test facilities. The objective of this study was to investigate the potential toxicity of ChAdOx1.5T4 to BALB/c mice when administered by intra-muscular injection on 2 occasions with a 14 day interval followed by a 13 day observational period. One group comprising ten male and ten female mice have received 55 µL of ChAdOx1.5T4 (1 x 10¹⁰ vp) into the right hind limb on Day 1 and Day 15. The control group consisting of five male and five female mice have received phosphate buffered saline (PBS), at the same volume-dose as the treated group. During the study, clinical conditions, body weight, food consumption, haematology (peripheral blood), blood chemistry, organ weight, macropathology and histopathology investigations were undertaken.

There was no effect of treatment on bodyweight gain or food consumption. There was no effect of treatment on blood chemistry parameters. Haematological examination on Day 28 revealed slightly higher group mean neutrophil and lymphocyte counts for treated males and females when compared with control males. This resulted in a slightly higher group mean total white blood cell count for treated animals. Values for other parameters, some of which attained a level of statistical significance were considered to be within the expected ranges for mice of this age and strain. There was no effect of treatment on blood chemistry parameters.

There were no unscheduled deaths during the study. There were no clinical findings and no reaction to treatment at the dose site during the course of the study. It was concluded that treatment with ChAdOx1.5T4 was well tolerated and was not associated with any adverse effects.

ChAdOx1.5T4 -MVA.5T4 prime boost vaccination regime in combination with anti-PD-1 monoclonal antibody

Previously, we have shown that the ChAdOx1-MVA vaccine encoding the prostate-associated antigen STEAP1 in combination with PD-1 blockade enhances efficacy and significantly improves survival of mice in the TRAMP-C1 subcutaneous tumour model³⁴. Further research has been conducted to assess the immunogenicity and tumour protective efficacy of ChAdOx1-MVA 5T4 vaccine as a single agent and in combination with checkpoint blocking antibodies. First, we have demonstrated that the vaccine alone mediated complete protection against challenge with the B16 tumour cell line expressing 5T4 antigen in a prophylactic setting. However, in a therapeutic setting the tumour progression has been modestly delayed, so we have evaluated whether the vaccine efficacy can be improved by a combination with anti PD-1 mAb³⁵. In a typical experiment, C57BL/6 mice were challenged with B16.h5T4 cells and primed with ChAdOx1.h5T4 or MVA.h5T4 vectors, or were left untreated (naïve mice). One week after, mice received MVA.h5T4 boost and PD-1 or isotype control antibodies intraperitoneally (i.p.). A comparative efficacy of the vaccine and PD-1 blockade as monotherapies and their combinations is shown in Figure 6 A,B. Firstly, blockade of PD-1 on its own offered just marginally better survival over isotype control mAb. As expected, ChAdOx1-MVA vaccine on its own delayed tumour progression to some extent. Notably, the administration of this vaccine in combination with anti-PD-1 was significantly more effective at suppressing tumour growth and prolonging survival of challenged mice than ChAdOx1-MVA vaccination used as monotherapy. In comparison, B16.h5T4 challenged mice prime-boosted with the MVA.5T4 vector, succumbed to tumours at the same time as naïve controls. Importantly, the analysis of IFNy responses in PBMCs isolated from the different groups demonstrated no effect of anti PD-1 therapy on the magnitude of h5T4-specific T cell responses in circulation, suggesting that anti PD-1 antibodies are acting at the tumour site (Figure 6C).

[figure not shown]

Figure 6. Heterologous ChAdOx1-MVA h5T4 vaccination regime in combination with anti PD-1 therapy significantly improves survival in B16.h5T4 melanoma tumour model compared with homologous MVA h5T4 vaccination combined to anti PD-1 therapy

C57BL/6 mice were challenged subcutaneously with 0.5×10^6 B16.h5T4 cells and immunised intramuscularly with 10^7 IU of ChAdOx1.h5T4 or 10^6 pfu of MVA.h5T4. One week later, mice were boosted with 10^6 pfu of MVA.h5T4 with PD-1 antibody or isotype control antibody. Naïve control mice were challenged and given only antibodies (IgG or PD-1) at the timepoint for boosting immunisation. Tumour size was measured three times per week and volumes were calculated as described above. Representative data of two biological replicate experiments are shown. (A) Tumour growth kinetics for each group expressed by mean tumour volume \pm SEM. (B) Kaplan-Meyer survival curves of the different groups of mice. (C) Graph shows representative data of ex vivo blood ELispot performed after prime-boost immunisations in the different groups of mice. Bars represent median spot forming cells (SFC) per 10^6 PBMCs.

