A new class of anti-cancer drugs termed immune checkpoint inhibitors (CPIs) has recently emerged. These belong to a category of antigen non-specific immunotherapies, in contrast to Provenge and PROSTVAC. The immune system is capable of recognising and eliminating cancer but it is held in check by inhibitory receptors and ligands. These immune checkpoint pathways, which normally maintain self-tolerance and down-regulate immune responses to pathogens to limit collateral tissue damage, can be co-opted by cancer to evade immune destruction. The novel drugs are the molecules that interrupt these immune checkpoint pathways and thus unleash anti-tumour immunity. The monoclonal antibodies (mAbs) against CTLA-4 (Cytotoxic T-lymphocyte-associated antigen 4), PD-1 (Programmed Death-1) and PD-L1 (Programmed Death Ligand-1) are the first drugs having entered the clinic as immunotherapies, and they have been licenced for advanced melanoma, lung, bladder, kidney cancers and other cancer types^{6,7}.

It is noteworthy that cancer types with the highest response rate to PD-1 blockade are the ones with the highest mutational load. Mutated proteins can give rise to neoantigens that are likely to be recognized by the host immune system and generate a spontaneous anti-tumour immune

response. Prostate cancer is known to have a relatively low mutational burden and this may, at least in part, explain the observation that checkpoint inhibitors have shown limited clinical benefit in prostate cancer to date^{8,9}. However, the data from the ongoing KEYNOTE-199 study (NCT02787005) reported (by de Bono et al.) at the ASCO annual meeting in June 2018 (abstract number 5007) demonstrate that anti PD-1 therapy had clinical activity in 11% of 258 metastatic castration-resistant prostate cancer patients. These drugs are even more likely to be clinically effective in prostate cancer if they are delivered in combination with an immunogenic vaccine, thus circumventing the need for tumour-specific neoepitopes in order to induce spontaneous anti-tumour immune responses.

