Encouragingly, the first meaningful evidence of PD-1 clinical activity in advanced metastatic prostate cancer has recently emerged. Graff and colleagues enrolled 27 men with mCRPC progressing on the androgen receptor antagonist enzalutamide (ENZ) and treated them with anti-PD-1 mAb pembrolizumab. Five of the 27 treated patients demonstrated a strong response to the treatment, with a 99% PSA reduction and observed shrinkage of measurable tumour lesions (ESMO 2017).

A large multi-centre international trial, KEYNOTE-199, to evaluate pembrolizumab as a monotherapy in 370 patients with metastatic castration resistant prostate cancer previously treated with docetaxel-based chemotherapy is currently ongoing (NCT02787005). Groundbreaking preliminary results from 258 patients already recruited to the trial were reported by De Bono and colleagues at the ASCO annual meeting in June 2018 (J Clin Oncol 36, 2018 (suppl; abstr 5007). It was demonstrated that pembrolizumab has antitumour activity in both PD-L1 positive and PD-L1 negative patients with mCRPC, as shown in the figure below. Across all cohorts, disease control rate lasting \geq 6 months was 11% in both RECIST-measurable and non-measurable disease.

Metastatic castration-resistant prostate cancer is genetically heterogeneous and includes DNA repair defective subtypes. DNA repair defects were suggested to be associated with pembrolizumab anti-tumour activity in this study. These data support further evaluation of anti PD-1 therapy in mCRPC and, in particular, in combination with vaccines that would provide a tumour-associated antigen as an alternative to naturally occurring mutated antigens.

Change From Baseline in Sum of Target Lesions, Cohorts 1+2

^aPercentages are calculated out of the [163 patients](#) who had ≥ 1 post-baseline scan evaluable per RECIST v1.1 by independent, central review. Data cutoff date: Oct 13, 2017.

Presented By Johann De Bono at 2018 ASCO Annual Meeting

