In ADVANCE, we are targeting a 25% or greater response rate to the vaccine in combination with PD-1 blockade in mCRPC patients. The sample size of 24 patients in Group 2 will require that 6 out of 24 treated patients will have complete response, partial response or stable disease. The patient cohorts recruited to the KEYNOTE-199 study will serve as a control group for ADVANCE and 11% overall response rate to PD-1 blockade as a monohterapy will be compared with the response rate to the vaccine in combination with anti-PD-1 treatment in the ADVANCE patients. If six of 24 treated patients do respond as described the would be a significantly ($P < 0.05$, two-tailed) higher rate than in the KEYNOTE-199 series and suggest added value to use of the viral vectors, supporting their assessment in a future larger scale trial.

Route of injection

The choice of the intramuscular route for ChAdOx1 vector is based on the assumption that no co-infection of natural human adenovirus could occur at this site. Furthermore, there is a large body of data from human clinical trials using replication defective Ad5- and Ad6-based HIV vaccines injected intramuscularly showing an excellent safety profile, no viral shedding, and high levels of immunogenicity. MVA.5T4 will also be given by the intramuscular route following data from [name] showing enhanced immunogenicity and less local reactivity (study VAC033) when MVA vectors are administered via the intramuscular compared to subcutaneous route.

Anti-PD-1 monoclonal antibody will be administered by intravenous infusion as per the SmPC.

[figure not shown]
Vaccine and immune checkpoint inhibitor dose

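### Section 2.2 says without condition that 6 of 24 responders would be significantly above KEYNOTE-199 (two-tailed P < 0.05); the result is borderline and depends on choices the protocol does not state

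*Protocol*

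**What the plan says.** Section 2.2 sets the Group 2 aim: "we are targeting a 25% or greater response rate to the vaccine in combination with PD-1 blockade in mCRPC patients". With 24 patients this is put as six with complete response, partial response or stable disease. The comparator is external: "The patient cohorts recruited to the KEYNOTE-199 study will serve as a control group for ADVANCE and 11% overall response rate". The significance claim follows. "If six of 24 treated patients do respond as described", the rate would be a "significantly ($P < 0.05$, two-tailed) higher rate than in the KEYNOTE-199 series", which would suggest that the vectors add value and would support a larger trial. The sentence names no test and does not mention uncertainty in the 11%.

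The protocol describes the 11% in three ways:

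- Section 2.1 reports that "anti PD-1 therapy had clinical activity in 11% of 258 metastatic castration-resistant prostate cancer patients".
- Section 2.2 calls the data "preliminary results from 258 patients already recruited to the trial" and gives the figure as a disease control rate with a minimum duration: at least "6 months was 11% in both RECIST-measurable and non-measurable disease".
- The comparison in section 2.2 calls it an overall response rate: "11% overall response rate to PD-1 blockade as a monohterapy will be compared".

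No responder count is given. Section 9.1 repeats the 25%, the 6 of 24 and the 11%, but not the P value.

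**The concern.** A series of 258 patients that serves as a control group is a sample, and its 11% carries sampling error. With only 24 patients on the other side, a result of 6/24 lies close enough to the 5% boundary that the treatment of the 11% and the choice of test decide which side it falls on. The sentence presents the outcome as settled.

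Six of 24 is the only numerical group-level efficacy benchmark in the protocol. Someone who later sees six responders could cite section 2.2 as having established significance in advance, when other standard analyses of the same data would not show it.

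**Working it through.** **Inputs.** 6 of 24 and 11% (sections 2.2 and 9.1); 25% target (same sections); 258 patients (sections 2.1 and 2.2). *Assumption:* the KEYNOTE-199 responder count is 28 or 29. These are the only counts of 258 that round to 11%: 27/258 = 10.5%, 28/258 = 10.9%, 29/258 = 11.2%, 30/258 = 11.6%.

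**Step 1. Reproduce the stated P < 0.05 with 11% as a known constant.**

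- Exact binomial: for X ~ Bin(24, 0.11), P(X ≥ 6) = 0.0417. The minimum-likelihood two-sided P adds lower-tail outcomes no more probable than the one observed. P(X = 0) = 0.89^24 = 0.061 exceeds P(X = 6) = 0.029, so nothing is added and the two-sided P is also 0.0417.
- Score test: z = (0.25 − 0.11)/√(0.11 × 0.89/24) = 0.14/0.0639 = 2.19, P = 0.028.

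Both reproduce the claim. Other two-sided conventions against the same constant do not:

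- Doubled exact tail: 2 × 0.0417 = 0.083.
- Continuity-corrected z: (0.14 − 0.5/24)/0.0639 = 1.87, P = 0.062.

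The 95% intervals for 6/24 divide in the same way: Clopper-Pearson (9.8% to 46.7%) contains 11%, Wilson (12.0% to 44.9%) does not. Rounding of the 11% matters too: the exact P is 0.034 at 10.5% and 0.0502 at 11.5%.

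**Step 2. Treat KEYNOTE-199 as a sample of 258.** For 28/258 the table is 6, 18 against 28, 230. The uncorrected chi-square is 282 × (6 × 230 − 18 × 28)² / (24 × 258 × 34 × 248) = 4.14, with a smallest expected count of 24 × 34/282 = 2.89. For 29/258 it is 3.82, with a smallest expected count of 2.98.

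| Two-sided P for 6/24 | vs 28/258 | vs 29/258 |
|---|---|---|
| Fisher exact | 0.0525 | 0.096 |
| Chi-square, Yates | 0.088 | 0.103 |
| Chi-square, uncorrected | 0.042 | 0.0505 |
| Fisher mid-P | 0.034 | 0.075 |

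Of these, only uncorrected chi-square and mid-P at 28/258 fall below 0.05. Fisher's one-sided P is 0.0525 or 0.060. The two-sided value jumps at 29 because the outcome of zero responders then becomes less probable than six, and its probability of 0.036 is added to 0.060.

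**Step 3. Other denominators in section 2.2.** With the 163 patients in the figure note, only 18/163 rounds to 11%: Fisher 0.093, uncorrected chi-square 0.056. With the full planned 370 (39 to 42 responders), Fisher runs from 0.043 to 0.058, but results are reported for 258.

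**Step 4. What the benchmark delivers.** Against a fixed 11%, at least 6/24 has one-sided alpha 0.042, and its probability at a true 25% is 0.578. The exact 95% interval for 28/258 is 7.3% to 15.3%. If the monotherapy rate lies in that range and the vaccine adds nothing, the chance of at least 6/24 runs from 0.7% to 15%. For 29/258 (7.7% to 15.7%) it runs from 0.8% to 16%.

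**The case against.** The strongest reply is that the figure is right. Section 2.2 quotes one number, 11%, and two ordinary two-sided tests against it give P < 0.05; uncorrected chi-square at 28/258 agrees. This stands, and a reader who infers an arithmetic error would be wrong. A reader might also infer that the claim holds only if 11% is taken as exact. The working does not support that either: a constant is not sufficient (doubled tail 0.083) and not strictly necessary (chi-square at 28/258).

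Secondly, the choice of test belongs in the statistical analysis plan, which section 9.2 promises, and sections 7.1 to 7.3 name Fisher's test only for comparisons between study arms. This is fair: the absence of a named test is no fault here, and Fisher's test is not prescribed for this comparison. But the sentence already asserts a result, and naming a test later would not make an unconditional assertion correct.

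Thirdly, the two-sample results rest on an assumed count, and one patient moves Fisher from 0.0525 to 0.096. That is true. It supports calling the result borderline; it does not support stating significance without condition.

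Fourthly, the wording is cautious rationale, section 9.1 drops the P value, and sections 5.7 and 8.7 leave continuation to the data and safety monitoring committee. This stands and limits the weight of the point.

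**Conclusion.** The significance claim is overstated. On the protocol's own description of KEYNOTE-199 as a control group, Fisher's test and the Yates-corrected chi-square exceed 0.05 at both counts compatible with 11% of 258, and uncorrected chi-square straddles it (0.042 or 0.0505). Against a fixed 11% the result still depends on the two-sided convention, from 0.028 to 0.083 across the tests shown.

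The point is minor to moderate: no stopping or continuation rule uses the P value, and the sample size need not change. A reader might infer that the threshold must rise to 7/24. The documents do not require that. It is a design choice that would bring Fisher's P to 0.018 or 0.021 but lower the probability of success at a true 25% from 58% to 39%.

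The two-sample figures rest on the assumed 28 or 29 responders. All the figures presuppose that ADVANCE responders are counted as the 11% was. Section 2.2 leaves this open: it attaches a minimum of 6 months to the KEYNOTE-199 disease control rate but no duration to stable disease in ADVANCE.

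**What to change.** In section 2.2, replace the unqualified two-tailed claim with text stating that:

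- 6/24 is an exact binomial benchmark against a fixed 11%, with one-sided alpha about 0.042 and a 58% probability of being reached at a true 25%;
- this ignores sampling error in a preliminary estimate;
- 6/24 does not reach two-sided P < 0.05 by Fisher's exact test against 28 or 29 of 258, the counts assumed from the rounded 11%;
- the alpha applies only if responders are counted in ADVANCE as they were for the 11%.

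Reconcile the two descriptions of disease control in section 2.2 so that the last condition can be judged. If the benchmark stays in section 9.1, carry the same description there.

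The cost is a few sentences and no patients. The stated significance becomes somewhat less favourable. Moving to 7/24 is optional and not part of this change.

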2.4. Previous clinical experience with MVA.5T4 vaccine

An MVA vector expressing the 5T4 antigen has been developed by Oxford BioMedica Ltd under the trade name of TroVax®. TroVax® has been administered to over 600 cancer patients. 12 studies of TroVax® in colorectal, renal and prostate cancer have been completed to date, and few serious adverse events have been attributed to TroVax® by investigators or the sponsor. Mild transient injection site reactions were reported in the majority of subjects together with mild transient pyrexia. No other notable, common or serious adverse events have been reported in studies using TroVax® as a single agent in heavily pre-treated subjects or in studies combining TroVax® with chemotherapy, interferon-α and IL-2^{15,36-41}.

Single agent studies

A single agent study (TV1) was conducted in 22 mCRC patients in objective response or stable disease (SD) 2.5 months after the end of first line chemotherapy. Four dose levels and two routes of administration (i.m. or i.d.) were tested in this study. TroVax® was well tolerated at all dose levels with a similar safety profile at each dose level. The highest dose level tested was 6.83×10^8 pfu. The safety profile was comparable to the usual safety profile of a vaccine. The main AEs considered to be related to TroVax®, all Grade 1, were injection site erythema and injection site reaction. Sixteen out of 17 patients evaluable for immune response had a cellular or humoral immune response. No radiological objective response was reported.

A second single agent study (TV-CR-UK) was conducted in 20 patients with resectable liver metastases of colorectal cancer. Patients received two injections before and after surgery. Two additional injections were administered in case of immune response. Sixteen out of 19 evaluable patients for immune response had a 5T4 cellular or humoral immune response prior to surgery. All 16 patients who completed four TroVax® injections and underwent surgery had a 5T4 cellular or humoral immune response after the surgery. Overall, taking into account immune response before and after surgery, 18 out of 19 evaluable patients had a 5T4 cellular or humoral immune response. The most common AE considered related to TroVax® was Grade 1-2 injection site reaction.

Combination studies

In colorectal cancer

Two Phase II combination studies were conducted in colorectal cancer (TV2-cr-ch-Oxaliplatin and TV2-cr-ch-Irinotecan studies). Chemotherapy did not abrogate the immune response to TroVax®. In both studies, the safety profile of TroVax® was similar to the safety profile reported in the single agent study. The safety profile of chemotherapy in combination with TroVax® was similar to the safety profile of chemotherapy alone.

In advanced renal cell cancer

Four Phase II and 1 Phase III studies were initiated in advanced renal clear cell cancer. One Phase II study assessed TroVax® in combination with interleukin-2 high dose (IL-2 HD) (TV2 Renal), 1 Phase II study of TroVax® in combination with IL-2 low dose (IL-2 LD) (TV-B2-001-05); 1 Phase I/II feasibility study of TroVax® with IFN- α (TV2-003-06); and 1 Phase II study of TroVax® with or without IFN- α (TV2-002-06).

A randomized Phase III double blind study was initiated in 2006 (TV3-001-06). This study compared TroVax® to placebo combined to standard of care (IL-2, IFN- α , sunitinib) in first line advanced (locally advanced or metastatic) renal clear cell cancer. The primary endpoint was overall survival; however, following the fourth interim review by the data safety monitoring board, the study was judged to be futile and was terminated early.

In hormone refractory prostate cancer

Three randomized Phase II studies were initiated in hormone refractory prostate cancer; one study evaluated TroVax® either alone or in combination with granulocyte macrophage-colony stimulating factor (GM-CSF) (TV-PHPRC-001-06), one study evaluated TroVax® plus docetaxel and docetaxel alone (PCa-07-101) but was stopped prematurely due to the termination of the TRIST study, and the third study (TV2-001-09) compared TroVax® plus docetaxel and docetaxel alone, but was also stopped prematurely owing to slow recruitment.

Overall conclusions from TroVax clinical studies

The administration of TroVax® is safe with mild to moderate vaccine reactions, chills, pyrexia, arthralgia and myalgia being the only adverse events of note. The safety profile of TroVax® is similar to that of a vaccine containing an attenuated vaccinia virus. The vector (MVA) has been widely used and no complications were reported when it was administered to over 120,000 subjects, including subjects at risk from vaccine complication. The safety profile of TroVax® allows combination with chemotherapy without increase in treatment toxicity and does not abrogate the immune response.

[figure not shown]
